Amifampridine dose will be titrated upward every 3 to 4 days, starting at 15 mg/day, at the discretion of the Investigator. Patients will either visit or have telephone/video contact with the site for each dose titration and at least one in-person site evaluation at Week 3 of the Runin period. When the Investigator determines that the patient has reached the maximal tolerable and efficacious dose, the patient should demonstrate they can remain on a stable dose and frequency for at least an additional 7 days. The Open-label Run-in period may be extended if additional time is needed for the dose titration. At the end of this period, patients must show at least a 3-point improvement in HFMSE score from start of Run-in, to be eligible for randomization (Day 0).

Randomization

Patients who continue to meet all the inclusion and exclusion criteria will be randomized on the last day of the Run-in period (Day 0).

Period 1 (Days 1-14) (± 1 day for each of Days 7 and 14)

Patients who have successfully completed the Open-label Run-in and continue to meet all inclusion/exclusion criteria will be randomized (1:1 ratio) on Day 0 to receive either

Page 27

amifampridine tablets (10 mg as amifampridine phosphate) or placebo tablets for 14 days, under double-blind conditions, (blinded medication to start after assessments obtained on open-label medication, on Day 0). Test medication will be dispensed by the Catalyst designee, according to the randomization schedule provided by Sponsor. All unused medication and the container must be brought back to the study site at each clinic visit. Safety and efficacy assessments will be made, in the site clinic, on Days 7 and 14 as detailed in the Schedule of Assessments in Table 1 and Section 12 STUDY Procedures.

Period 2 (Days 15-28) (±1 day for each of Days 21 and 28)

Following the in-clinic assessments on Day 14 of Period 1, the Period 1 study medication is collected and the patient should be given the blinded Period 2 medication; either amifampridine phosphate or placebo tablets (whichever they did not receive in Period 1) for 14 days. The Period 2 medication is to start with the next dose after the assessments are performed on Day 14 with Period 1 medication.

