12.2 Open-label Run-in

Amifampridine dose will be titrated upward every 3 to 4 days, starting at 15 mg/day, at the discretion of the Investigator. Patients will either visit or have telephone/video contact with the site for each dose titration and at least one in-person site assessment at Week 3 of the Run-in period (Table 1). When the Investigator determines that the patient has reached the maximal tolerable dose, the patient should demonstrate they can remain on a stable dose and frequency for at least an additional 7 days. The Open-label Run-in period may be extended if additional time is needed for dose titration. At the end of this period, patients must show a ≥3-point improvement in HFMSE from start of Run-in, to be eligible for randomization (Day 0).

Patients should be given a Drug Dosing Diary to record each dose of their open-label medication and instructions on how to complete the form.

Additional visits are allowed as necessary. Screening visit and start of Run-in (Day 1) may be combined into a single visit.

12.3 Period 1

12.3.1 Day 0

Patients who are deemed eligible for continuation will have the assessments/procedures listed below completed on Day 0 after taking a supervised dose of their medication for that day during the clinic visit, so that the assessments can occur in the prescribed relation to the time of medication administration.

- Confirmation of Inclusion/Exclusion criteria;
- Assessment of AEs/SAEs;
- Complete physical exam with weight;
- Vital signs (seated position), including SBP, DBP, heart rate, respiration, and body temperature;
- Standard resting 12-lead ECG;
- Clinical laboratory tests including hematology, chemistry, and urinalysis;
- Urine pregnancy test in females of childbearing potential only;
- Concomitant medications;
- Collect patient Drug Dosing Diary and perform IP accountability of open-label medication;
- Efficacy assessments following in-clinic dose of open-label medication as listed below:

Order of Assessment at Each Study Visit (when applicable)	Start Time After Dose (+ 10 minutes unless otherwise specified)
HFSME	45 minutes
6-minute walk test	After HFSME
Time to rise from floor	After 6-minute walk
Time to rise from chair	After rise from floor
Time to climb 4 stairs	After rise from chair
Time to walk 10 meters	After climb stairs
Quality of Life Assessment	After 10-meters walk

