# 10.10.2 Duration of Treatment and Compliance

Duration of treatment during the open-label period will be summarized for the Safety Population. The duration of treatment during the open-label run-in period is the date of Day 0 minus date of first study dose+1.

Duration of treatment during the double-blind periods will be summarized for the Safety Population by treatment and by period and pooled.

For Period 1, the duration of treatment is the (date of Day 14 minus date of Day 0)+1; for patients who discontinue during Period 1, the duration of treatment during Period 1 is the (date of the last dose during Period 1 minus the date of Day 0) +1.

For Period 2, the duration of treatment is the (date of Day 28 minus date of Day 14)+1; for patients who discontinue during Period 2, the duration of treatment during Period 2 is the (date of the last dose during Period 2 minus the date of Day 14)+1.

The overall duration during the double-blind periods will be obtained for each treatment by adding the durations for the periods during which the patient received each treatment.

Compliance is 100%\*(Number consumed)/(Number prescribed). "Number consumed" is from Study Drug Accountability and "Number prescribed" is number of tablets to have been taken daily duration.

Compliance during the double-blind periods will be summarized for the Safety Population by treatment and by period. The compliance during the double-blind periods will be obtained for each treatment by performing the same calculations for the periods during which the patient received each treatment.

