**Table 1 - Categories of Severity for Adverse Events** 

Severity	Description	
Grade 1	Mild; asymptomatic or mild symptoms; clinical or diagnostic observations only; intervention not indicated.	
Grade 2	Moderate; minimal, local or noninvasive intervention indicated; limiting age-appropriate instrumental ADL*.	
Grade 3	Severe or medically significant but not immediately life-threatening; hospitalization or prolongation of hospitalization indicated; disabling; limiting self-care ADL**.	
Grade 4	Life-threatening consequences; urgent intervention indicated.	Note: Grade 4 and 5 adverse events should
Grade 5	Death related to AE.	always be reported as serious adverse events

Activities of Daily Living (ADL)

\* Instrumental ADLs refer to preparing meals, shopping for groceries or clothes, using the telephone, managing money, etc.

\*\*Self-care ADLs refer to bathing, dressing and undressing, feeding self, using the toilet, taking medications, and not bedridden.

A treatment-emergent adverse event (TEAE) is any AE that emerges after randomization having been previously absent, or worsens relative to the previous periods. All AEs will be coded using the Medical Dictionary for Regulatory Activities (MedDRA), Version 23.0. All treatment-emergent adverse events (TEAEs) will be summarized by the treatment at the time of onset. Counts and percentages will be presented by treatment for each observed system organ class (SOC) and preferred term (PT) as defined in MedDRA. A patient having more than one TEAE with the same PT in a given time period will be counted only once in the incidence calculation for that PT for that time period. Similarly, if a patient has more than one TEAE in the same SOC in a given time period, the patient will be counted only once in the total number of patients with a TEAE for that SOC for that time period. TEAEs will summarized only for the treatment at onset unless it worsens at subsequent period(s) or recurs after having resolved at a previous period; in each of these situations, the TEAE will be considered a new TEAE and summarized for both treatments.

Each TEAE will be assessed with respect to severity and relationship to treatment. The relationship of an AE will be recorded using the specified relationship categories described in Table 2.

Table 2 - Description of relationship to adverse events categories

Relationship	
Category	Description
Not Related	Exposure to the IP has not occurred
	OR

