	The administration of the IP and the occurrence of the AE are not
	reasonably related in time
	OR
	The AE is considered likely to be related to an etiology other than the
	use of the IP; that is, there are no facts [evidence] or arguments to
	suggest a causal relationship to the IP.
Possibly	The administration of the IP and the occurrence of the AE are
Related	reasonably related in time
	AND
	The AE could be explained equally well by factors or causes other
	than exposure to the IP.
Probably	The administration of IP and the occurrence of the AE are reasonably
Related	related in time
	AND
	The AE is more likely explained by exposure to the IP than by other
	factors or causes.

The following summary tables will be provided:

1. An overview of TEAEs including the number of TEAEs, related TEAEs, TESAEs, related TESAEs, TEAEs leading to premature discontinuation, TEAEs leading to hospitalization, life-threatening TEAEs, number of patients with at least one TEAE, at least one related TEAE, at least one TESAE, at least one TEAE leading to premature discontinuation, at least one TEAE leading to hospitalization, at least one life-threatening TEAE, and at least one TEAE leading to death

- 2. Summary of all TEAEs by treatment group, Primary SOC and PT
- 3. Summary of all related TEAEs by treatment group, Primary SOC and PT
- 4. Summary of all TESAEs by treatment group, Primary SOC and PT
- 5. Summary of all related TESAEs by treatment group, Primary SOC and PT
- 6. Summary of all TEAEs leading to hospitalization by treatment group, Primary SOC and PT
- 7. Summary of all life-threatening TEAEs by treatment group, Primary SOC and PT
- 8. Summary of all TEAEs leading to premature discontinuation by treatment group, Primary SOC and PT
- 9. Summary of all TEAEs by treatment group, Primary SOC and PT and maximum severity

The following individual data listings will be produced:

- 1. A listing of all TEAEs
- 2. A listing of all TESAEs
- 3. A listing of all IMP related TEAEs
- 4. A listing of all IMP related TESAEs
- 5. A listing of all TEAEs leading to hospitalization
- 6. A listing of all life-threatening TEAEs
- 7. A listing of TEAEs leading to premature discontinuation
- 8. A listing of all TEAEs leading to death
- 9. A listing of all AEs started before the first dose of study drug intake
- 10. A listing of all AEs started after the first dose of study drug intake but before the date of randomization (Day 0)

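### TEAEs start at randomization, not at the first blinded dose, so some Day 0 adverse events fall between the AE listings and others count as double-blind events before any blinded drug is taken

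*SAP*

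**What the plan says.** **TEAE start.** SAP 10.12.1: "A treatment-emergent adverse event (TEAE) is any AE that emerges after randomization having been previously absent", or one that worsens relative to previous periods.

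**Assignment.** SAP 10.12.1: "All treatment-emergent adverse events (TEAEs) will be summarized by the treatment at the time of onset". No rule is given for a day on which two treatments are taken.

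**Listings.** Of the ten AE listings in SAP 10.12.1, listings 1 to 8 cover TEAEs or subsets of them. Listing 9 is "A listing of all AEs started before the first dose of study drug intake". Listing 10 is "A listing of all AEs started after the first dose of study drug intake but before the date of randomization (Day 0"). All nine AE summary tables are TEAE tables.

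**Day 0.** Under Protocol 12.3.1, procedures are "completed on Day 0 after taking a supervised dose of their medication for that day". That dose is open-label: "Efficacy assessments following in-clinic dose of open-label medication as listed below". Randomization comes last in the list of procedures, and blinded drug starts once all Day 0 assessments are finished.

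**Day 14.** Protocol 9.1.1: "The Period 2 medication is to start with the next dose after the assessments are performed on Day 14 with Period 1 medication". Protocol 12.3.2 says the same.

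**General promises.** SAP 10.2 and 10.12 and Protocol 14.5 say that all collected data, all observed safety data and all AEs, respectively, will be listed.

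**The concern.** The TEAE definition is tied to an administrative act (randomization), whereas exposure changes at a later dose. Listing 10 is tied to a calendar date, whereas the TEAE definition refers to an event within that date. The two limits do not meet on Day 0, and that is a day when a dose is supervised and AEs are assessed.

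Safety and tolerability against placebo is a primary objective. The protocol synopsis restricts the safety analysis to TEAEs, so the TEAE boundary decides which events enter the comparison and on which side. In a trial of about 12 patients, one or two misplaced events can visibly change an incidence table. If no rule is written down, the choice is left to the programmer or to the data review.

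**Working it through.** No sample-size or power figure is involved. The check sets the rules against the order of events.

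**Inputs**
- About 12 patients, 6 per sequence (SAP 6.1). AP is amifampridine then placebo; PA is placebo then amifampridine.
- HFMSE starts 45 minutes after the clinic dose (Protocol 9.3.3).
- Eligibility needs the Day 0 HFMSE (exclusion criterion 8), so randomization cannot come before it.
- Time to peak concentration is about 38 minutes fasted and 78 minutes fed (Protocol 7.4.1). Dose-related events can therefore plausibly begin between the clinic dose and randomization.
- Non-serious AEs are reportable from the first dose of study drug (Protocol 10.1), so a Day 0 event is reportable.

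**Step 1: Day 0 onsets against the listings.** Listings 9 and 10 exclude every Day 0 onset: listing 9 because study drug has already been taken, listing 10 because the date is not before Day 0. A new Day 0 event is listed only if it is a TEAE, which depends on how the phrase about randomization is read:

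| Day 0 onset | By date and time | Date later than Day 0 | Date Day 0 or later |
|---|---|---|---|
| After clinic dose, before randomization | in none of the ten | in none of the ten | TEAE |
| After randomization, before first blinded dose | TEAE | in none of the ten | TEAE |
| After first blinded dose | TEAE | in none of the ten | TEAE |

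The first reading is the literal one. It leaves the pre-randomization window uncovered. An event from that window that persists unchanged does not become a TEAE later, because it was neither previously absent nor worse. The second reading widens the gap. The third closes it by counting events on open-label drug as double-blind TEAEs.

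**Step 2: which drug has been taken.** A is amifampridine, P is placebo:

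| Sequence | Day 0 clinic dose, then next | Day 14 clinic dose, then next |
|---|---|---|
| AP | A, then A | A, then P |
| PA | A, then P | P, then A |

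An event after randomization but before the first blinded dose is a TEAE under the literal reading, while the only drug taken is open-label A. In AP patients the drug label would still be correct. In the roughly 6 PA patients the event could be shown under placebo if treatment is read as the assigned Period 1 treatment.

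**Step 3: Day 14 under a whole-day rule**, if only dates are available:

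| Rule | AP | PA |
|---|---|---|
| All of Day 14 to Period 1 | P events after the switch shown under A | A events after the switch shown under P |
| All of Day 14 to Period 2 | A events before the switch shown under P | P events before the switch shown under A |

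Either rule can misplace events in both directions. The plan's date arithmetic does not settle it. Protocol 9.1.1 labels the periods Days 1–14 and 15–28. The exposure formulas in SAP 10.10.2 count Day 14 twice (Period 2: "For Period 2, the duration of treatment is the (date of Day 28 minus date of Day 14)+1"): (14 − 0) + 1 = 15 and (28 − 14) + 1 = 15, a sum of 30 days over the 29 calendar days from Day 0 to Day 28. Those formulas measure duration and do not assign AEs, so they illustrate the ambiguity without creating an error in the AE tables.

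**Step 4: size per patient.** Assume denominators of about 12 per treatment. One patient wrongly present in a column changes that incidence by 1/12 = 8.3 percentage points. If the patient's only event of that preferred term moves from one column to the other, the difference changes by 2/12 = 16.7 points. The effect is smaller or nil if the patient has another event of the same term in the same column, because patients are counted once per term per period.

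**The case against.** The best case for the plan is that it assigns events by treatment at the time of onset, not by date. Read that way, an AP patient's event between the Day 14 clinic dose and the first Period 2 dose belongs to amifampridine, and nothing in SAP 10.12.1 credits a Day 0 event before any blinded dose to placebo. The synopsis also places the start of Period 2 after the Period 1 clinic dose and the end-of-Week-2 evaluations. Onset times may exist: SAP 14 gives a date-and-time output format and sorts listings by date and hours where applicable, and the Dosing Diary records each dose. This stands. It reduces the Day 14 point to a condition, because neither document says that AE onset time is collected or used.

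A reader might go further in four ways that the documents do not support:

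- **That Day 0 events are lost.** The general promises mean they should be listed somewhere. What remains is a contradiction between those promises and the ten listings meant to carry them out, and the events are still in no table.
- **That Day 14 events also escape the listings.** A new Day 14 event is after randomization on any reading, so it is in listing 1.
- **That drug events move systematically to placebo and shrink the safety contrast.** That needs a date-only rule the SAP does not state, and Step 3 shows errors in both directions.
- **That the 43% oral paresthesia rate in the food-effect study indicates the number affected.** Those were healthy volunteers given single 20 mg doses. Patients here have been titrated and have held a stable dose for at least 7 days before Day 0, and an ongoing event at unchanged severity is not a new TEAE.

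**Conclusion.** The Day 0 defect is in the text. The TEAE start and the limit of listing 10 leave an uncovered window before randomization, and the window between randomization and the first blinded dose counts as treatment-emergent although only open-label amifampridine has been taken. The Day 14 point is conditional: the stated rule is sound if onset can be placed relative to the first Period 2 dose, and undefined if only dates are available.

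The number of affected events is probably small, since the windows are short and patients are on a tolerated, stable dose. The documents give no rate from which to estimate it. The per-patient effect of up to 8.3 points in one column assumes about 12 patients per treatment and no other event of the same term in that column. The point also assumes that the next scheduled dose usually falls on the same day, which is likely with 3 or 4 doses a day. It is worth correcting because the rule is wrong as written and costs little to change; it does not threaten the trial.

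**What to change.** In SAP 10.12.1:

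1. Define a TEAE as an AE that starts or worsens at or after the first dose of blinded drug.
2. Extend listing 10 to all AEs that start after the first open-label dose and before the first blinded dose, Day 0 included.
3. State that on Day 14 the treatment at onset changes at the first Period 2 dose, using onset time, or a before/after-first-new-dose indicator, where available.
4. For AEs on Day 0 or Day 14 with unknown timing, flag them in the listing, set one default before unblinding, and show the AE counts under the alternative assignment.

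The default should not be to assign an event to amifampridine whenever either treatment that day was amifampridine. The table in Step 2 shows this is true of every patient on both dates, so no untimed switch-day event could ever count as placebo. It would also conflict with item 1, by crediting blinded amifampridine to PA patients who have not yet received it.

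The cost is a few lines of SAP text, a little programming and, if not already collected, a before/after-dose indicator for two dates. SAP 4 already provides for review and revision before the unblinded analyses.

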## 10.12.2 Vital Signs and Body Weight

Vital signs, including sitting blood pressure (systolic and diastolic; mmHg), sitting heart rate (beats/minute), body temperature (°C), respiration rate (breaths/minute), and weight (kg) will be summarized using descriptive statistics by sequence and period for both the observed values and CFB. Height will be recorded at Screening visit only.

BMI will be calculated at Screening visit according to the following formula:

 $BMI(kg/m^2) = ((body\ weight\ (kg)/(height\ (m))^2).$ 

Height and BMI will be summarized using descriptive statistics by sequence.

#### 10.12.3 12-Lead ECG

Analysis will be performed in the SAF analysis set.

A standard 12-lead ECG will be recorded at Screening, Days 0 and Day 28 visit.

Each tracing will be classified as "Normal tracing", "Abnormal tracing (not clinically significant)", "Abnormal tracing (clinically significant)", or "Unknown".

A summary of the assessments will be provided by sequence and period. Clinically significant changes from baseline will be recorded as AEs.

ECG abnormalities reported will be coded using MedDRA thesaurus version 23.0, and the terms listed for all enrolled patients.

#### 10.12.4 Physical Examination

Summary analysis will involve the SAF analysis set.

A complete physical examination is to be performed at Screening, Days 0, and Day 28.

These assessments will be summarized by sequence and period using counts and percentages.

All verbatim terms reported in the Physical Examination form will be assigned to a Preferred Term (PT) and will be classified by the primary System Organ Class (SOC) according to the Medical Dictionary for Regulatory Activities (MedDRA) thesaurus, version 23.

A summary table containing the frequency and percentage of patients who exhibited at least one abnormality as well as of the abnormalities reported at Screening, Day 0 and Day 28 by primary SOC and PT will be prepared by treatment sequence.

Physical examination abnormalities will be listed for all patients.

# 10.12.5 Laboratory Tests

For blood chemistry and hematology, descriptive statistics will be presented for the observed value and CFB by sequence and visit. The frequency and percentage of patients who experience abnormal (i.e. outside of reference ranges) laboratory values and clinically significant abnormalities will be presented by sequence and visit.

Moreover shift tables from screening to each time-point, with regard to the laboratory normal range (low, normal and high), will be presented for all parameters of blood chemistry and hematology by sequence. The laboratory parameters to be collected are given below in Table 3.

**Table 3 - Clinical Laboratory Tests** 

Blood Chemistry	Haematology	Urine Tests
Albumin	Haemoglobin	Appearance
Alkaline phosphatase	Haematocrit	Color
ALT (SGPT)	WBC count	pН
AST (SGOT)	RBC count	Specific gravity
Direct bilirubin	Platelet count	Ketones
Total bilirubin	Differential cell count	Protein
BUN		Glucose
Calcium		Bilirubin
Chloride		Nitrite
Total cholesterol		Urobilinogen
$CO_2$		Hemoglobin
Creatine phosphokinase		
Creatinine		
Glucose		
GGT		
LDH		
Phosphorus		
Potassium		
Total protein		
Sodium		
Uric acid		

Urinalysis parameters will not be included in summary tables.

All laboratory parameters will be listed for all patients.

